6.9 Safety and Efficacy Assessments

Safety will be assessed by the Investigator from history and clinical examination. Adverse events (AE) will be recorded in the CRFs and in part 2 of the study, a comparison will be made between the number, type and severity of AEs between the treatment groups.

Comfort will be assessed on the basis of the patient diary cards. A comparison of the total comfort scores between the randomised treatment groups in part 2 of the study, will be made at the conclusion of the trial. For each treatment group a total comfort score of < 10 will be deemed to be comfortable/acceptable, 10 - 19 will be moderately uncomfortable, 20 - 29 will be very uncomfortable and > 30 will be severely/unacceptably uncomfortable.

Composite eye sign and symptom scoring will be carried out by the investigator/blind assessor (depending on the part of the study) at each scheduled clinic visit. Symptoms will be scored by the patient in response to specific questioning by the investigator/blind assessor. Signs will be scored by the investigator/blind assessor as a result of the clinical examination. At each visit the patient will be asked which eye feels to be the worst affected at the time of the visit and that eye will be used for the examination. If both eyes seem to the patient to be equally affected the right eye will always be used. The worst affected eye may change from visit to visit.

For each sign/symptom a numerical score 0 - 3 will be awarded (see table in Section 17.1 (AKC and VKC) and 17.2 (severe allergic conjunctivitis - SAC or PAC). These scores will be summed at the conclusion of the examination and this will be known as the composite score. The minimum possible composite score is 0, the maximum 33 (AKC and VKC) or 27 (severe allergic conjunctivitis (SAC or PAC)). All statistical comparisons, in part 2 of the study, will be done on the basis of the composite score for each patient/visit.

MMP-9 detection using the *Inflammadry*[®] device. This device will give a binary (positive/negative) result which will be recorded in the CRFs at each time point and a comparison of the numbers of positives in each randomised treatment group will be made.

Tear film break up time (TBUT). Tear breakup time (TBUT) is a clinical test used to assess for evaporative dry eye disease. To measure TBUT, fluorescein is instilled into the patient's tear film and the patient is asked not to blink while the tear film is observed under a broad beam of cobalt blue illumination. The TBUT is recorded as the number of seconds that elapse between the last blink and the appearance of the first dry spot in the tear film. A TBUT under 10 seconds is considered abnormal.

This test will be performed in one eye only at the time points specified in the Schedule of Events.

6.9.1 Clinical scoring

Clinical scoring will be according to the method described by Akpek (Akpek et al. 2004). This will be carried out at each clinic visit by the PI or his designated sub-investigator(s). A composite score of 5 symptoms and 6 signs will be used for AKC and VKC patients, and a composite score of 4 symptoms and 5 signs will be used for patients with severe allergic conjunctivitis - SAC or PAC. One eye only should be scored which will be the eye judged as worst affected at each visit by the patient. In the event that the patient judges both eyes to be equally affected the right eye will be assessed. Scoring will be on a scale of 0 to 3 where 0 is unaffected, 1 is mildly affected, 2 is moderately affected and 3 is severely affected (see Section 17.1 and 17.2 for full details). The maximum possible score for symptoms and signs combined is 33 (AKC/VKC) or 27 (severe allergic conjunctivitis). To qualify for entry to the trial patients must score:

AKC or VKC - a minimum of 18 at the Screening visit.

The following symptoms will be scored:

- 1. Itching
- 2. Tearing
- 3. Discomfort (burning, stinging or foreign body sensation)
- 4. Discharge
- 5. Photophobia

The following signs will be scored:

- 1. Bulbar conjunctival hyperaemia
- 2. Tarsal conjunctival papillary hypertrophy
- 3. Punctate keratitis
- 4. Neovascularisation of cornea
- 5. Cicatrising conjunctivitis
- 6. Blepharitis

Severe allergic conjunctivitis - SAC or PAC - a minimum of 15 at the Screening visit.

The following symptoms will be scored:

- 1. Itching
- 2. Tearing
- 3. Discomfort (burning, stinging or foreign body sensation)
- 4. Photophobia

The following signs will be scored:

- 1. Upper tarsal conjunctival hyperaemia
- 2. Upper bulbar conjunctival hyperaemia
- 3. Chemosis
- 4. Upper tarsal conjunctival papillae
- 5. Blepharitis

6.9.2 Patient diary card

All patients will be issued with a diary card and will be asked to score comfort on a scale of 0 to 4 as shown in Table 5 below. The patient may make further comments (e.g. a difference in comfort between the two eyes) in the diary card.

| | Table 5 | Eye comfort scoring |
|--|---------|---------------------|
|--|---------|---------------------|

| Score | Description |
|-------|---|
| 0 | Perfectly comfortable |
| 1 | Slight discomfort. Aware of some burning, itching or stinging for up to half a minute after using the eye drop, solution but the discomfort improves without treatment. |
| 2 | Moderate discomfort. Burning, itching or stinging lasts for half a minute or longer but improves without treatment. |
| 3 | Severe discomfort. Burning, itching or stinging last for at least half a minute and requires washing the eyes to relieve it. |
| 4 | Unbearable burning itching or stinging. So severe that you cannot continue treatment. |

Scoring will be carried out at 0.5, 1, 2, 3 and 5 minutes after instillation of the drops and, in addition, patients will be asked to insert a brief description (up to 5 words) of how the eyes feel at the 3-minute time point. A list of suggested descriptor words will be provided but patients will be free to use any terminology they wish. Suggested descriptors are:

- Normal, cool, comfortable, smooth, fresh
- Uncomfortable, gritty, dry, sticky
- Burning, itchy, stinging, painful

In addition, there will be space for any other comments the patient may have.

Diary cards will be checked by the trial nurse or the PI/blind assessor at each visit to ensure that they are being filled in correctly and regularly.

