17.1 Scoring of Clinical Signs and Symptoms – AKC and VKC

| SYMPTOM | 0 | 1 | 2 | 3 |
|--|-------------------------------------|---|--|---|
| ltch | No desire to rub or scratch the eye | Occasional desire to rub or scratch the eye | Frequent need to rub or scratch the eye | Constant need to rub or scratch the eye |
| Tearing | Normal tear production | Positive sensation of fullness of the conjunctival sac without tears spilling over the lid margin | Intermittent, infrequent spilling of tears over the lid margin | Constant, or nearly constant, spilling of tears over the lid margins |
| Discomfort (including burning, stinging, and foreign body sensations) | Absent | Mild | Moderate | Severe |
| Discharge | No abnormal discharge | Small amount of mucoid discharge noted in the lower cul-de-sac | Moderate amount of mucoid discharge noted in the lower cul-de- sac and in the marginal tear strip; presence of crust upon awakening | Eyelids tightly matted together upon awakening, requiring warm soaks to pry lids apart; warm soaks necessary to clean eyelids during the day |
| Photophobia | No difficulty experienced | Mild difficulty with light causing squinting | Moderate difficulty, necessitating dark glasses | Extreme photophobia, causing the patient to stay indoors; cannot stand natural light even with dark glasses |
| SIGN | 0 | 1 | 2 | 3 |
| Bulbar conjunctival hyperaemia | Absent | Mild | Moderate | Severe |
| Tarsal conjunctival papillary hypertrophy | No evidence of papillary formation | Mild papillary hyperaemia | Moderate papillary hypertrophy with oedema of the palpebral conjunctiva and hazy view of the deep tarsal vessels | Severe papillary hypertrophy obscuring the visualization of the deep tarsal vessels |
| Punctate keratitis (superficial epithelial keratitis and punctate staining of the cornea with fluorescein) | No evidence of punctate keratitis | One quadrant of punctate keratitis | Two quadrants of punctate keratitis | Three or more quadrants of punctate keratitis |
| Neovascularization of cornea (new vessel formation, crossing the limbus onto the clear cornea by 2 mm) | No evidence of new vessel Formation | Presence of neovascularization in 1 quadrant of cornea | Presence of neovascularization in 2 quadrants of cornea | Presence of neovascularization in 3 quadrants of cornea |
| SIGN | 0 | 1 | 2 | 3 |

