6.10.2 Secondary Endpoints

6.10.2.1 Post-instillation comfort

Post-instillation comfort scores will only be available for the least comfortable eye. The eye that the scoring was recorded on will not be captured on the eCRF.

A score of 0 to 4 will be recorded at 0.5 min, 1 min, 2 min, 3 min and 5 min each morning and evening on diary card.

The total score over two-week periods for days 1 to 14, 15 to 28, 29 to 42 and 43 to 56 will be calculated for each patient by summing the scores from the five timepoints taken each morning and evening over the 14 days, therefore the total score will have a possible range of 0 to 560. If there are 20 or more missing data points during the period, then the total score will not be calculated and set to missing.

For derived non-missing scores, an average score for the period will also be calculated as follows:

$$Average \ score = \frac{Total \ score}{Number \ of \ non - missing \ days}$$

The average score at each two week-period will be classified as follows: an average total comfort score of < 10 will be deemed to be comfortable/acceptable, 10 - 19 will be moderately uncomfortable, 20 - 29 will be very uncomfortable and ≥ 30 will be severely/unacceptably uncomfortable.

The number and percentage of missing data over the two-week period will be calculated, where 140 data points would expected to be recorded over 14 day period.

Should the five scores not be available at any morning or evening timepoint there will be no imputation, and the total score and classification will be derived for the two-week period for that patient regardless of missing data.

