6.10.2.1.2 Analysis

The classification of the average daily post-instillation comfort score will be analysed using an ordinal logistic regression model. The model will include treatment and visit as fixed effects and a treatment-by-visit interaction.

The following variance/covariance matrix structures for the repeated visits by a patient will be assessed: Compound symmetry, 1st order autoregressive, Toeplitz and unstructured. The variance/covariance matrix structure that results in the smallest Akaike information criterion (AIC), indicating the best model fit will be selected.

Assumptions about the proportionality of odds will also be assessed by appropriate methods such as by fitting fixed and random effects at each partition and testing the equality of the effects at different partitions. Should assumptions not hold, then the treatment odds ratios for the individual cumulative levels of the variable will be presented.

The adjusted least squares (LS) estimate for the treatment odds ratio (nomacopan:Placebo) along with corresponding 95% CI will be presented for each treatment period.

A null hypothesis of no change in classification of total post-instillation comfort score at Days 43 to 56 between treatment groups (nomacopan/Placebo) will be assessed and a p-value will also be reported.

The extent of missing data will be taken into consideration when analysing the total score data. Should it be felt appropriate, alternative analysis may be carried out and/or

sensitivity analyses using imputation methods such as last observation carried forward will also be considered.

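### Post-instillation comfort is rated only after the drop and modelled without a baseline term, so its fixed classes mix disease discomfort with drop effect, and background spread goes unadjusted

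*Protocol*

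**What the plan says.** **Timing.** Protocol 6.9.2: "Scoring will be carried out at 0.5, 1, 2, 3 and 5 minutes after instillation of the drops". SAP 6.10.2.1 agrees: "A score of 0 to 4 will be recorded at 0.5 min, 1 min, 2 min, 3 min and 5 min each morning and evening". Neither document asks for a rating just before instillation. The Schedule of Events (Protocol 17.3) first lists diary cards at Day 7 for the Part 1 patients and at Day 14 for Part 2, so no baseline comfort score is scheduled.

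**Scale.** Table 5 in Protocol 6.9.2 runs from 0 (full comfort) to 4 (unbearable). Grade 1 is tied to the drop: "Aware of some burning, itching or stinging for up to half a minute after using the eye drop". Grade 2 is not explicitly tied to it: "Moderate discomfort. Burning, itching or stinging lasts for half a minute or longer but improves without treatment". Protocol 6.9.1 scores much the same sensations as disease symptoms in both patient groups: itching, and "Discomfort (burning, stinging or foreign body sensation").

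**Analysis.** SAP 6.10.2.1 sums the ratings over each 14-day period, divides by the number of days with data, and puts the result into four fixed classes: "an average total comfort score of < 10 will be deemed to be comfortable/acceptable", followed by 10 to 19, 20 to 29, and 30 or more. SAP 6.10.2.1.2 fits an ordinal logistic regression to the classes: "The model will include treatment and visit as fixed effects and a treatment-by-visit interaction". The SAP models for visual acuity (6.10.2.2.2), clinical score (6.10.2.3.2) and tear film break up time (6.10.2.5.2) each include the baseline value as a covariate. Comfort is the one modelled secondary endpoint that does not.

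**The concern.** A patient whose eyes itch and burn from the disease can record that discomfort at every post-drop time. The recorded score is then background discomfort plus whatever the drop adds. Three things follow.

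- The classes are read in absolute terms, from acceptable to unacceptable, yet disease alone can place a patient in any of them.
- The trial hopes that the drug relieves symptoms (Protocol 5.1). If it does, the relief lowers the comfort score while a sting raises it, and the two can offset each other. The tested interval is Days 43 to 56, when any relief would have had time to develop.
- Patients differ in background discomfort. Part 2 has up to 16 patients and no stratification (SAP 4), and the model removes none of that variation.

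**Working it through.** **1. The plan's own figures.** Inputs from SAP 6.10.2.1: 5 times, 2 sessions a day, 14 days, maximum grade 4.

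- Ratings per period: 5 × 2 × 14 = 140.
- Maximum total: 140 × 4 = 560.

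Both match the SAP. The daily maximum is 5 × 2 × 4 = 40. A steady grade *b* at every rating gives a daily average of 10*b*.

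**2. Classes reached with no sting.** The background grade is an assumption, shown over a range.

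| Steady background grade | Daily average | 14-day total | SAP class |
|---|---|---|---|
| 0 | 0 | 0 | comfortable (<10) |
| 0.5 | 5 | 70 | comfortable (<10) |
| 1 | 10 | 140 | moderately uncomfortable (10–19) |
| 2 | 20 | 280 | very uncomfortable (20–29) |
| 3 | 30 | 420 | worst class (≥30) |

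**3. The same sting in two patients.** Assume that the drop adds 1 grade at two of the five times, in both sessions: 1 × 2 × 2 = +4 a day. With background 0 the score is 4 (comfortable). With background 1 it is 10 + 4 = 14 (moderately uncomfortable). A one-grade difference in background moves the score by 10 a day, which is 10 / 4 = 2.5 times this sting.

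**4. Masking between arms.** If the drug lowers background by *d* grades at each rating, the net difference from placebo is sting − 10*d*, provided background has room to fall.

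- Sting +4 a day: 4 − 10 × 0.4 = 0, so a fall of 0.4 grade cancels it.
- Sting of 1 grade at one time only, +2 a day: 2 − 10 × 0.2 = 0, so a fall of 0.2 grade cancels it.

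**5. How far the entry criteria imply background discomfort.** The thresholds (Protocol 4.1) average 18 / 11 = 1.64 and 15 / 9 = 1.67 per item out of 3. That average covers signs as well as symptoms. Signs alone can reach 6 × 3 = 18 and 5 × 3 = 15, exactly the thresholds, though only if every sign is at its maximum. Background discomfort is therefore likely in many patients but not guaranteed in each, which is why the table starts at 0.

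**6. What the existing ratings can still show.** Take the 0.5-minute grade minus the 5-minute grade within a session. Steady background gives *b* − *b* = 0 at any *b*. The sting in step 3 gives (*b* + 1) − *b* = 1 per session, or 2 a day, whatever the background (short of the ceiling at 4). Summing the five times discards this contrast.

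**7. How many patients could still supply a pre-drop rating.** The justification for Amendment 7, Change 4 puts randomised recruitment at 50% of plan. That leaves 16 × 0.5 = 8 patients, about 4 per arm. SAP 6.2 rules out testing with fewer than 5 results in either group.

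**The case against.** **The randomised contrast is valid.** The placebo is the same formulation without the drug (Protocol 3.1), so background disease is balanced in expectation and the difference between arms estimates the net effect on post-drop comfort. This stands. A reader might infer that the comfort comparison is invalid; it is not. But a net effect is not sting alone if the drug also changes symptoms, and discomfort caused by the vehicle is common to both arms and so does not appear in the contrast.

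**Relevant data exist.** A reader might infer that nothing collected could separate disease from drop. The documents do not support that: itch and discomfort are scored in clinic on Day 1 and at later visits, and the diary records a profile from 0.5 to 5 minutes. What stands is that the comfort analysis uses neither.

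**Table 5 is not a plain symptom scale.** Its grades refer to duration, the need to wash the eyes, and inability to continue, and grade 1 refers to the drop. How a patient with constant itch would answer is uncertain, so step 2 shows what can happen and does not forecast it. For the same reason the present wording would not suit a rating made before the drop.

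**Status and power.** Sample size was set on practical grounds (Protocol 11.4), and secondary results are to be read as patterns (Protocol 11.5). Low power is declared and is not held against the diary here. A reader might also take comfort to be the trial's main tolerability outcome. It is one of five secondary endpoints; the primary endpoint is ocular treatment-emergent adverse events.

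**Conclusion.** The point holds as a limit on interpretation and a missed adjustment, not as a failure of the comparison. It is certain from the text that ratings are made only after the drop, that the scale overlaps with disease symptoms, that the five times are summed into absolute classes, and that the model has no baseline term. By arithmetic, background discomfort of grade 1, 2 or 3 fills the second, third or fourth class with no sting, and a +4 a day sting is hidden by a 0.4-grade fall in background. The size in this trial rests on two assumptions that the documents do not settle: how patients with ongoing symptoms use Table 5, and how large the sting and the symptom relief are. The primary adverse-event analysis is not touched.

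**What to change.** **SAP 6.10.2.1.2.** Add the sum of the Day 1 itch and discomfort item scores (each 0 to 3, so 0 to 6, and common to both patient groups) as a covariate in the comfort model, in line with the other modelled secondary endpoints. State in advance what will be reported if the model does not converge with it.

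**SAP 6.10.2.1.** Report the 0.5-minute minus 5-minute score by arm and period as a supportive measure of transient sting. State that the comfort classes include background disease discomfort and are not a measure of drop effect alone.

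**Optional, Protocol 6.9.2.** For patients still to be enrolled, add one rating just before each drop, with wording suited to a pre-drop state. Report it descriptively, given the numbers in step 7.

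**Cost.** The two SAP changes need no new data, only a few sentences before unmasking. The covariate adds one parameter to a small ordinal model. It can reduce noise from baseline differences, but it cannot remove an effect of the drug on symptoms during treatment. The early-minus-late difference misses a sting that lasts past 5 minutes, and it could also reflect the drop soothing the eye. Separation therefore stays partial. The optional rating needs a diary reprint and one more entry per dose.

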6.10 Laboratory Tests

The following laboratory tests will need to be conducted at the applicable visits, per Schedule of Events. The assessments will be conducted at the central laboratory, as indicated in the following table:

Table 6Laboratory Tests

| | - |
|-------------|---|
| Central Lab | |
| | |

PK (Unbound rVA576) Anti-Drug Antibody (ADA) PD (CH50) The analyses will be performed in masked fashion as far as the Central; Lab is concerned and unmasking will not be performed until the conclusion of the trial.

6.11 Medical Photography

For better assessment of the eye, medical photography may be performed at investigator's judgement and photographs of both eyes may be obtained during the evaluation of the composite score and related ocular adverse events. During the consent obtained at screening the patients will be allowed to opt out of the medical photography. Declining consent for medical photography will not impact patient's participation in the study. Patient's confidentiality will be protected during medical photography of the eye.

7 REASON FOR WITHDRAWAL / EARLY DISCONTINUATION

7.1 Termination or Suspension of the Study

The Sponsor may prematurely terminate or suspend the study at any time for the following reasons:

- Safety concerns e.g. due to occurrence of many serious ADRs
- Achieving the purpose of the study is considered impossible e.g. due to inadequate recruitment of patients

The Sponsor may prematurely terminate or suspend the study as well at a particular medical institution at any time during the course of the study, if major violations/deviations of the protocol or other procedures have not been improved or International Committee on Harmonisation (ICH) GCP has not been followed.

If the study is prematurely terminated or suspended, the Sponsor should promptly inform the Investigators. The Investigator or designee should promptly inform the participating patients and change the study medication to other appropriate therapy(ies). All supplies must be returned.

The Investigator may prematurely terminate or suspend the study at their medical institution with the agreement of the Sponsor. This may be done at any time during the study if they consider that ensuring patient safety during the study is difficult due to safety concerns (e.g., occurrence of many SAEs).

The party which terminates the study will provide a written statement as to the reason for the termination.

The Sponsor (or CRO) will notify Regulatory Authorities, as appropriate of premature terminations or other suspensions. The Investigator or their designee should promptly inform the corresponding Ethics Committee (EC).

7.2 Withdrawal Criteria

In accordance with applicable regulations, a patient has the right to withdraw from the study at any time and for any reason without prejudice to their future medical care by the physician or at the Institution. Should a patient withdraw from the study, the patient will not undergo any further study-specific procedures or receive any treatment mandated by the protocol.

If a patient fails to attend scheduled trial assessments, the Investigator must determine the reasons and the circumstances as completely and accurately as possible.

In the event of the premature withdrawal of a patient from the trial, the end of trial visit should be carried out as completely as possible. Minimally, a safety assessment should be performed.

In the case of withdrawal due to the occurrence of unacceptable toxicity, the patient will be requested to remain under the supervision of the Investigator until the toxicity has resolved or is no longer considered to be clinically significant by the Investigator.

If an AE classified as severe results in patient withdrawal from the study, the patient will be followed until the AE (or SAE) resolves or stabilises, and any interventions required to resolve or stabilise the event will be recorded in the eCRF.

All withdrawals must be documented in the eCRF. A patient may be withdrawn in any of the following circumstances:

- Withdrawal of consent (mandatory withdrawal)
- Intake of non-permitted concomitant medications (may be discussed with the Sponsor and dependent on the nature of the medication)
- Patient is non-compliant with more than three consecutive missed doses and two missed clinic visits, in the opinion of the Investigator (discretionary withdrawal)
- If discontinuation is considered necessary by the Investigator and/or Sponsor (mandatory withdrawal)
- Request of Regulatory Agency (mandatory withdrawal)
- Patient develops an illness that would compromise his participation in the study (may be discussed with sponsor)
- Pregnancy

